3.0 Introduction

This Statistical Analysis Plan (SAP) was created based on Study Protocol M14-496 Amendment 3 dated 03 June 2019.

This statistical analysis plan describes the statistical analyses to be completed by the Data and Statistical Science Department for Study M14-496. It provides the details to further elaborate statistical methods as outlined in the protocol before the Part 1 database lock. However, features of the study and the data collected may suggest that deviations from the approach presented in this analysis plan are appropriate, and exploratory analyses can be added. A detailed description of any substantive modifications to this SAP will be included in the final clinical study report (CSR). Serum adalimumab (ADA) concentration and anti-ADA antibodies (AAA) will be studied by a pharmacokinetics group, the corresponding analysis plan is documented separately and is not in the scope of this SAP. A final CSR is planned after the study is completed.

Unless noted otherwise, all analyses will be performed using SAS version 9.2 or later (SAS Institute Inc., Cary, NC 27513) under the UNIX operating system.

4.0 Study Background

4.1 Objective

The primary objective is to compare the effectiveness based on the achievement of minimal disease activity (MDA) at Week 16 between subjects who had ADA introduced and those that had methotrexate (MTX) escalated to the highest recommended dose of 20 - 25 mg every week (ew) or highest tolerable dose up to 25 mg ew after inadequate disease control on the initial MTX therapy.

The secondary objectives are:

- To compare the effectiveness at Week 16 between subjects who had ADA introduced and those that had MTX escalated to the highest recommended

dose of 20 - 25 mg ew or highest tolerable up to 25 mg ew based on the following clinical, functional and quality of life measures:

- Psoriatic Arthritis Disease Activity Score (PASDAS)
- Disease Activity in Psoriatic Arthritis (DAPSA) score
- Psoriatic Arthritis Impact of Disease (PsAID) score
- American College of Rheumatology (ACR) 20/50/70 response
- Disease Activity Score 28 (DAS28)-CRP
- Psoriasis Area and Severity Index (PASI)
- Health Assessment Questionnaire Disability Index (HAQ-DI)
- Short Form Health Survey 36 (SF-36) scores: physical component summary (PCS) and mental component summary (MCS)
- Dermatology Life Quality Index (DLQI)
- Leeds Enthesitis Index (LEI)
- Tender dactylitic digit count
- To evaluate the achievement of MDA at Week 32 on each of the four different treatment groups involving ADA and/or MTX in Part 2 of the study.

4.2 Study Design

4.2.1 Study Design and Design Diagram

This interventional Phase 4 open-label, randomized, controlled, parallel-group, multicenter study will be conducted in two (2) parts, each of 16-week duration.

Part 1 (Day 1 - Week 16) is to compare the achievement of MDA on ADA introduced in combination with MTX versus MTX alone escalated to the highest recommended dose of 20 - 25 mg ew^{1,2} or highest tolerable dose up to 25 mg ew, whatever feasible, in PsA subjects inadequately controlled after the initial course of MTX at 15 mg ew. Part 1 will be open-label, randomized, controlled, parallel group.

Part 2 (Week 16 - 32) is to evaluate the effectiveness of four (4) different treatment regimens consisting of ADA and/or MTX in maintaining or attaining MDA, as applicable.

Part 2 will be open-label, parallel group. Subjects will be assigned into the four treatment arms based on their MDA status at Week 16 and initial randomized treatment. Starting at Week 24, there will be rescue treatment option based on not achieving MDA and investigator's judgment.

The study is designed to enroll approximately 240 subjects at approximately 60 sites to meet scientific and regulatory objectives without enrolling an undue number of subjects in alignment with ethical considerations.

Following a screening period of up to 30 days, subjects meeting the selection criteria will be randomized in a 1:1 ratio to either of the two (2) arms and treated for 16 weeks in Part 1:

- Arm 1/Part 1: ADA 40 mg eow in combination with MTX 15 mg ew (ADA 40 mg eow + MTX 15 mg ew),
- Arm 2/Part 1: MTX escalated to 20 - 25 mg or highest tolerable dose ew (MTX 20 - 25 mg or highest tolerable dose ew).

After the assessment of MDA at Week 16 (primary endpoint), subjects will be assigned to one of the four (4) treatment arms based on the achievement of MDA and initial randomized treatment, and treated for additional 16 weeks in Part 2 as follows:

[figure not shown]
- Arm 1/Part 2: Subjects achieving MDA at Week 16 on ADA 40 mg eow plus MTX 15 mg ew, will have MTX completely withdrawn at Week 16 and continue receiving ADA as monotherapy (ADA 40 mg eow),
- Arm 2/Part 2: Subjects not achieving MDA at Week 16 on ADA 40 mg eow plus MTX 15 mg ew, will have ADA escalated to 40 mg ew in combination with MTX 15 mg ew (ADA 40 mg ew plus MTX 15 mg ew),
- Arm 3/Part 2: Subjects achieving MDA at Week 16 on MTX escalated to 20 - 25 mg or highest tolerable dose ew, will continue with the same MTX dose (MTX 20 - 25 mg or highest tolerable dose ew),
- Arm 4/Part 2: Subjects not achieving MDA at Week 16 on MTX escalated to 20 - 25 mg or highest tolerable dose ew, will receive ADA 40 mg eow in

combination with MTX 20 - 25 mg or highest tolerable dose ew (ADA 40 mg eow plus MTX 20 - 25 mg or highest tolerable dose ew).

Subjects in Arms 1 - 4 of Part 2 of the study will have the option of being rescued, starting at Week 24 and based on the subject not achieving MDA and the Investigator's judgment. The selection of the rescue treatment regimen will be at the discretion of the Investigator, but should involve ADA and/or MTX and should not involve prohibited medications per the protocol.

A schematic of the study design is shown below in [Figure 1](#):

Figure 1. A schematic of the study design

4.2.2 Variables used for Stratification at Randomization

Randomization was stratified by the duration of prior MTX treatment at 15 mg ew: ≤ 3 months and > 3 months.

4.3 Endpoint

4.3.1 Primary Efficacy Endpoint

The primary endpoint is the proportion of subjects achieving MDA at Week 16 on ADA 40 mg eow plus MTX 15 mg ew as compared with subjects on MTX alone escalated to 20 - 25 mg or highest tolerable dose ew.

MDA in PsA is defined as fulfilling at least 5 of the 7 following criteria:^{3,4}

- TJC ≤ 1 (out of TJC68 assessed in this study)
- SJC ≤ 1 (out of SJC66 assessed in this study)
- PASI ≤ 1 or BSA ≤ 3
- Patient's assessment of pain VAS ≤ 15
- Patient's global assessment of disease activity (PtGA) VAS ≤ 20
- HAQ-DI score ≤ 0.5
- Tender enthesal points ≤ 1 (out of 8 assessed in this study)

4.3.2 Secondary Efficacy Endpoints

The secondary efficacy endpoints include:

- At Week 16:
 - Change from baseline in PASDAS
 - Change from baseline in DAPSA score
 - Change from baseline in PsAID score
 - Proportion of subjects achieving ACR 20/50/70 response
 - Change from baseline in DAS28-CRP score

- Proportion of subjects achieving PASI 75/90/100 response (for subjects with BSA \geq 3% at baseline)
- Change from baseline in HAQ-DI score
- Changes from baseline in SF-36PCS and SF-36MCS
- Change from baseline in DLQI score
- Change from baseline in Leeds Enthesitis Index (LEI) (for subjects with presence of enthesitis at baseline)
- Change from baseline in tender dactylitic digit count (for subjects with presence of dactylitis at baseline)
- The proportion of subjects in MDA at Week 32.

4.3.3 Exploratory Efficacy Endpoints

Clinical Efficacy

Clinical efficacy outcomes listed under the secondary endpoints (refer to Section 4.3.2) will be analyzed as exploratory endpoints at Week 32 on the 4 different treatment regimens.

Ultrasound

- The change in Global OMERACT-EULAR synovitis score (GLOESS) from baseline to Week 16 in randomized treatment groups of Part 1 of the study.
- The change in OMERACT enthesitis score from baseline to Week 16 in randomized treatment groups of Part 1 of the study.
- The change in Global OMERACT-EULAR synovitis score (GLOESS) from Week 16 - 32 in the 4 arms of Part 2 of the study.
- The change in OMERACT enthesitis score from Week 16 - 32 in the 4 arms of Part 2 of the study.

4.3.4 Safety Endpoint

The following safety evaluations will be performed during the study: concomitant medication review, adverse event (AE) monitoring, vital signs, and laboratory tests.

4.3.5 Pharmacological Endpoint

For subjects receiving ADA, blood samples will be collected for determination of ADA serum concentrations and the presence of anti-ADA antibodies (AAA). Analysis will be conducted separately and not in the scope of this SAP.

4.4 Sample Size Justification

The study is powered to detect the difference in MDA response rates at Week 16 between ADA + MTX 15 mg and MTX escalated dose groups. Assuming an MDA response rate of 40% in the ADA + MTX group and 20% in the escalated MTX group, a total sample size of 240 subjects, 120 subjects per arm, will provide at least 90% power to detect the difference between the two treatment groups at a significance level of 2-sided 0.05, accounting for 10% dropout.

4.5 Part 1 Analysis

Part 1 database lock is planned when all randomized subjects have completed Week 16 of the study. The 16-week study results (through Week 16) will be based on this database lock.

4.6 Multiplicity Testing Procedures for Type-I Error Control

There is only one primary endpoint in this study and therefore multiplicity adjustment is not applicable.

4.7 Missing Data Imputation

The following missing data imputation will be performed for efficacy analysis.

Non-Responder Imputation (NRI) Approach

To account for missing data for the binary efficacy endpoints, a non-responder imputation approach (NRI) will be used, e.g., subjects who have missing data at a specific visit will be treated as non-responder for that visit, or who prematurely discontinue or have been rescued will be considered as a non-responder for all subsequent visits.

Mixed-Effects Model Repeated Measures (MMRM)

The repeated measure analysis will be conducted using mixed models based on observed data at all visits. For the MMRM analysis (of continuous variables), data collected after premature discontinuation of study drug will be excluded. The mixed model includes treatment, visit, treatment-by-visit interaction, and the stratification factor of duration of prior MTX use (≤ 3 months or > 3 months) as fixed effects, subject as random effect and baseline measurement as a covariate. An unstructured variance covariance matrix will be used. The parameter estimations assume data being missing at random (MAR) and using the method of restrictive maximum likelihood (REML).

Observed Cases (OC)

The OC analysis will not impute values for missing evaluations, and thus a subject who does not have an evaluation on a scheduled visit will be excluded from the OC analysis for that visit. In addition, OC will not include values after subject have rescue visit or after premature discontinuation of study drug.

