8.1.4.2 Analyses of Secondary Efficacy Variables

A complete list of secondary efficacy endpoints is provided in Section 5.3.3.2. Binary secondary endpoints in Part 1 will be summarized using count and percentages and will be compared between treatment groups using CMH test adjusting for the stratification factor of the duration of prior use of MTX.

MDA at Week 32 is a Part 2 endpoint and it will be summarized by four treatment regimens. No statistical testing will be performed.

For the continuous secondary endpoints, the change from baseline at Week 16 will be analyzed using MMRM with treatment, stratification factor of prior MTX use, visit, and

treatment-by-visit interaction as fixed effects, subject as random effect and baseline value as a covariate. The MMRM analysis is based on all observed data. The LS mean, 95% CI and standard error for each randomized treatment group, the LS mean of the treatment difference and its associated 95% CI and p-value from the MMRM model will be presented.

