6.3 Secondary Efficacy Analyses

Part 1 Analysis

A complete list of secondary efficacy endpoints is provided in Section 4.3.2. Binary endpoints will be analyzed in a similar way as the primary endpoint.

For the continuous endpoints, the change from baseline at Week 16 will be analyzed using MMRM with treatment, the stratification factor of duration of prior MTX use (≤ 3 months or > 3 months), visit, and treatment-by-visit interaction as fixed effects, subject as random effect and baseline measurement as a covariate. The MMRM analysis is based on observed data. The LS mean, 95% CI and standard error for each randomized treatment group, the LS mean of the treatment difference and its associated 95% CI and p-value from the MMRM model will be presented.

Long Term Analysis

The achievement of MDA at Week 32 on each of the four different treatment regimens will be evaluated. The proportion of subjects who achieved MDA at Week 32 will be summarized by counts and percentages for the four treatment regimens. Point estimate and 95% CI using normal approximation will be provided for each treatment regimen as well. The subjects who were rescued prior to Week 32 will be considered as non-

responders (MDA = 0) at Week 32. No comparison between treatment regimens will be performed.

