6.4 Other Efficacy Analyses

Clinical Efficacy Variables

Binary secondary endpoints described in Section 4.3.2 will be analyzed as exploratory endpoints at Week 32 using count and percentages on each of the four different treatment regimens. Point estimate and 95% CI using normal approximation will be provided as well. The data occurred after initiation of the rescue medication will be imputed using NRI for the subsequent visits in this summary.

Continuous secondary endpoints described in Section 4.3.2 will be analyzed as exploratory endpoints at Week 32 by summary statistics (number of subjects, mean, 95% confidence interval, standard deviation, median, minimum, maximum) for each treatment regimen. All observed data will be used to summarize the continuous exploratory endpoints. The data occurring after initiation of the rescue medication will be overwritten by the last observation prior to treatment rescue (Last observation carried forward: LOCF) for the subsequent visits in this summary.

Ultrasound Variables

For ultrasound assessment at Week 16, analysis will be performed using similar methods to those described for the secondary continuous efficacy endpoints. In addition, baseline weight will also be included as an additional covariate in MMRM. The LS mean, 95% CI and standard error for each randomized treatment group and the LS mean of the treatment difference, its associated 95% CI and p-values will be presented.

For the ultrasound assessment at Week 32, summary statistics (number of subjects, mean, 95% confidence interval, standard deviation, median, minimum, maximum) will be presented for each treatment regimen. All observed data will be used to summarize the

continuous exploratory endpoints. The data occurring after initiation of the rescue medication will be overwritten by LOCF for the subsequent visits in this summary.

Summary of Efficacy Endpoints by Visit

Summary of the primary and secondary efficacy endpoints at the scheduled time points will be presented by two treatment groups in the Part 1 analysis and by four treatment regimens in the long-term analysis. Achievement of each MDA component as binary endpoints will be summarized similarly as well.

For Part 1 analysis, binary efficacy endpoints will be analyzed in a similar way as the primary endpoint and continuous efficacy endpoints will be analyzed from the same MMRM model for the Wk16 endpoints.

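### The MMRM carries baseline as a main effect only, so one baseline slope serves all five Part 1 visits and the Week 16 comparison may lose precision; a baseline-by-visit term is an almost free improvement.

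*SAP*

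**What the plan says.** SAP 4.7 lists the fixed effects: "The mixed model includes treatment, visit, treatment-by-visit interaction, and the stratification factor of duration of prior MTX use". It continues with "subject as random effect and baseline measurement as a covariate. An unstructured variance covariance matrix will be used", and estimation is by REML under missing at random. SAP 6.3 applies the model to the continuous Week 16 secondary endpoints, with "visit, and treatment-by-visit interaction as fixed effects, subject as random effect and baseline measurement as a covariate". Protocol 8.1.4.2 gives the same terms, "treatment-by-visit interaction as fixed effects, subject as random effect and baseline value as a covariate", and does not name a covariance structure.

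SAP 6.4 extends the model to the Part 1 ultrasound endpoints, adding baseline weight, and to the by-visit results: "continuous efficacy endpoints will be analyzed from the same MMRM model for the Wk16 endpoints".

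Protocol 5.1.2.1 and Appendix C place the post-baseline Part 1 visits at Weeks 2, 4, 8, 12 and 16. SAP 4.3.2 names Week 16 as the visit for the continuous secondary endpoints. Neither document includes a baseline-by-visit term or explains its absence.

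**The concern.** The model lets the treatment effect differ at every visit but holds the baseline effect constant. For a change-from-baseline outcome, the slope on baseline depends on how strongly the visit value still correlates with baseline. If that correlation falls with time, the correct slope at Week 16 differs from the correct slope at Week 2. A single slope is a compromise, and the likelihood tends to set it from the early visits, where residual variance is smaller. Baseline variation that a Week 16 slope would have removed then stays in the Week 16 residual and widens the interval.

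At stake is the precision of the continuous Part 1 secondary endpoints and the exploratory Week 16 ultrasound endpoints.

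The wording raises a second, smaller question. A subject random effect is named next to an unstructured covariance matrix. Taken literally, the matrix already contains everything a random intercept could describe.

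**Working it through.** **Figures in the plan.** The documents give no power, SD or correlation for any continuous endpoint. The one power statement (protocol 8.2, SAP 4.4) concerns MDA: 40% versus 20%, 120 per arm, two-sided 0.05, 10% dropout, at least 90% power. It reproduces. With n per arm, power = Φ[(0.20√n − 1.96√(2·0.3·0.7)) / √(0.4·0.6 + 0.2·0.8)].
- n = 108 (10% removed): Φ[(2.078 − 1.270)/0.632] = 89.9%.
- n = 120: Φ[(2.191 − 1.270)/0.632] = 92.7%.

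That test is a CMH test with non-responder imputation and does not use the MMRM.

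**Precision at Week 16.** Everything below rests on assumed correlations.

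1. Scale the baseline SD to 1. Let ρ be the correlation of the visit value with baseline and σ the visit SD. The correct slope for change at a visit is β = ρσ − 1.
2. With visit-specific slopes, the Week 16 residual variance is V = σ²(1 − ρ²).
3. With one slope, generalised least squares gives b = (1′S⁻¹β)/(1′S⁻¹1), where S is the residual covariance including the misfit (β − b)(β − b)′, iterated to convergence.
4. The variance of the Week 16 treatment difference is then inflated by 1 + (β₁₆ − b)²/V.
5. A comparison with 80% power under visit-specific slopes keeps power Φ(2.80/√ratio − 1.96).

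Post-baseline correlations are taken as 0.85·exp(−0.02·weeks apart) in the first three rows and 0.90·exp(−0.03·weeks apart) in the rest. SD is constant except in the last row.

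| Baseline correlation, Week 2 to Week 16 | β₁₆ | b | V | Variance ratio | 240 behaves like | 80% power becomes |
|---|---|---|---|---|---|---|
| 0.5 throughout | −0.50 | −0.500 | 0.75 | 1.00 | 240 | 80% |
| 0.6 to 0.4 | −0.60 | −0.473 | 0.84 | 1.02 | 235 | 79.2% |
| 0.7 to 0.4 | −0.60 | −0.371 | 0.84 | 1.06 | 226 | 77.6% |
| 0.8 to 0.4 | −0.60 | −0.260 | 0.84 | 1.14 | 211 | 74.7% |
| 0.8 to 0.3 | −0.70 | −0.198 | 0.91 | 1.28 | 188 | 69.8% |
| 0.8 to 0.3, SD falling to 0.8 of baseline | −0.76 | −0.304 | 0.582 | 1.36 | 177 | 67.2% |

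For example, 0.7 to 0.4 gives 1 + (−0.60 + 0.371)²/0.84 = 1 + 0.0524/0.84 = 1.06. The common slope there matches the correct slope for Week 4 (−0.37), not the one for Week 16.

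**Simulation.** There were 600 replicates per pattern, 120 per arm, an unstructured covariance, missing-at-random dropout of about 5-7%, and no true treatment effect.

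| Pattern | Model | Mean estimate | Empirical SE | Model SE | Type I error |
|---|---|---|---|---|---|
| 0.7 to 0.4 | common slope | 0.0026 | 0.1304 | 0.1258 | 6.0% |
| 0.7 to 0.4 | baseline-by-visit | 0.0017 | 0.1243 | 0.1212 | 5.8% |
| 0.8 to 0.3 | common slope | −0.0002 | 0.1430 | 0.1438 | 4.8% |
| 0.8 to 0.3 | baseline-by-visit | 0.0009 | 0.1256 | 0.1265 | 4.7% |

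The model-based variance ratios are (0.1258/0.1212)² = 1.08 and (0.1438/0.1265)² = 1.29. The empirical ratios are 1.10 and 1.30. These agree with the table within simulation error. The Monte Carlo standard error of the type I error is √(0.05·0.95/600) = 0.9 points, so neither model departs from 5%.

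**Covariance wording.** Five visits give 5·6/2 = 15 distinct variances and covariances. An unstructured matrix plus a random-intercept variance has 16 parameters. The Jacobian has rank 15, so the intercept variance cannot be separated from the matrix. The implied marginal covariance is the same with or without it, and so is the Week 16 standard error.

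**The case against.** The strongest reply is that the stated model is valid. It kept its size and showed no bias in the simulation. It costs nothing if the baseline slope is constant, and nothing in the documents shows that it is not. The affected endpoints carry no power claim, and any loss widens the sponsor's own intervals. All of this stands. It makes the point an efficiency refinement, and the size must be given as a range. It does not supply a reason to keep the restriction, because removing it costs almost nothing.

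Three stronger readings are tempting, and the documents do not support them.

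- **That the random effect itself loses precision.** It does not, because the marginal covariance is unchanged. The phrase may also be shorthand for the subject block of the repeated-measures covariance; the SAP does not say. Read literally, the practical risk is a software warning or a failed fit.
- **That the protocol's silence on covariance means compound symmetry and a distorted type I error.** Protocol 8.1.2 leaves the full analysis detail to the SAP, and SAP 4.7 specifies an unstructured matrix. The SAP fills the gap, so the two documents do not conflict.
- **That the common slope biases the comparison through missing data.** The simulation included missing-at-random dropout, and the mean estimates stayed near zero. Its dropout was below the 10% the plan allows for, but nothing in it points to bias.

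**Conclusion.** The point holds as a minor one. The model shares one baseline slope across five visits, and this can cost precision at Week 16. The variance inflation is nil with a flat baseline correlation, about 2-8% with a mild to moderate decline and about 10-30% with a steep one. These figures rest on assumed correlations among visits and, for the ranges, a roughly constant SD. They are not bounds: a falling SD took the steep case to 36%. The documents cannot show which case applies, and it may differ between endpoints.

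The analysis is not invalid. The primary MDA comparison does not use this model. The random-effect wording is an ambiguity to clear up and has no effect on the Week 16 standard error.

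**What to change.** In SAP 4.7 and 6.3, and in the by-visit and ultrasound paragraphs of 6.4, add the interaction of baseline value with visit as a fixed effect. This uses 4 more degrees of freedom (five slopes in place of one) with about 240 subjects. Fewer contribute to the enthesitis and dactylitis endpoints, which SAP 4.3.2 restricts to subjects affected at baseline, and to the optional ultrasound assessments. If the slopes prove equal, essentially nothing is lost.

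In the same edit, replace the phrase about subject as a random effect with a statement that within-subject correlation is modelled only through the unstructured covariance matrix, with no separate random intercept. It would also help to name a fallback structure in case the unstructured fit does not converge, since none is given.

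The cost is a few lines of SAP text and one model statement. Protocol 8.1.2 leaves analysis detail to the SAP, so a protocol amendment is not needed for this alone.
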